9.1. Single reference safety document

The **CCI** [REDACTED] SAFETY REPORTING LANGUAGE: OTHER PRIMARY DATA COLLECTION STUDY (A type) will serve as the single reference safety document during the course of the study, which will be used by Pfizer safety to assess any safety events reported to Pfizer Safety by the investigator during the course of this study.

10. PLANS FOR DISSEMINATING AND COMMUNICATING STUDY RESULTS

The study results will be submitted to domestic or international academic journal.

COMMUNICATION OF ISSUES

In the event of any prohibition or restriction imposed (e.g., clinical hold) by an applicable Competent Authority in any area of the world, or if the investigator is aware of any new information which might influence the evaluation of the benefits and risks of a Pfizer product, Pfizer should be informed immediately.

In addition, the investigator will inform Pfizer immediately of any urgent safety measures taken by the investigator to protect the study patients against any immediate hazard, and of any serious breaches of this NI study protocol that the investigator becomes aware of.

12. LIST OF TABLES

Table 1. Evaluation Criteria [15,20-21]

13. LIST OF FIGURES

None

ANNEX 1. LIST OF STAND ALONE DOCUMENTS

None

ANNEX 2. ENCEPP CHECKLIST FOR STUDY PROTOCOLS

Not applicable

ANNEX 3. ADDITIONAL INFORMATION

Not applicable

**VERSION HISTORY**

[figure not shown]
Version	Effective Date	Change Type (New, Revise, Admin)	Summary of Revisions
1.0	12-MAR-2020	New	Not Applicable

PFIZER CONFIDENTIAL

## 1 INTRODUCTION

This statistical analysis plan (SAP) is presented to report the statistical methods used and results obtained in the treatment satisfaction comparison in rheumatoid arthritis patients between tofacitinib citrate and adalimumab, each used in rheumatoid arthritis treatment. The purpose of this observational study is to report the comparison of treatment satisfaction and quality of life in patients with rheumatoid arthritis treated with tofacitinib citrate or adalimumab.

CCI

*When the contents of*

*the rht protocol are referenced, it is identified in italics.*

The documents below were reviewed for preparation of the SAP.

- “Treatment satisfaction comparison in rheumatoid arthritis patients between tofacitinib citrate and adalimumab, each used in rheumatoid arthritis treatment”  
Protocol version 3.0
- “Treatment satisfaction comparison in rheumatoid arthritis patients between tofacitinib citrate and adalimumab, each used in rheumatoid arthritis treatment”  
Medical records version 3.0
- “Treatment satisfaction comparison in rheumatoid arthritis patients between tofacitinib citrate and adalimumab, each used in rheumatoid arthritis treatment”  
Patient questionnaires version 1.0

[figure not shown]
CCI

The purpose of this SAP is to describe the plans outlined to complete the Statistical Analysis Report (SAR) for “Treatment satisfaction comparison in rheumatoid arthritis patients between tofacitinib citrate and adalimumab, each used in rheumatoid arthritis treatment.” Statistical analyses confirmed in this SAP could be used in future manuscripts for academic publication of the study outcomes.

*Rheumatoid arthritis (RA) is a chronic inflammatory autoimmune disease that causes joint destruction and leads to loss of function, decreased quality of life [1], and ultimately death [2] from complications. It is characterized by an excessive increase in pro-inflammatory cytokines that causes abnormal inflammation [3]. Therefore, the American Arthritis Foundation has recommended early diagnosis and appropriate treatment*

PFIZER CONFIDENTIAL

*targeting maintenance of low disease activity or remission of RA, prevention or delay of joint damage, and recovery of physical abilities and improvement in the quality of life [4].*

*According to the 2016 Update of the European League Against Rheumatism (EULAR) recommendation, the basic principle of the RA treatment goal is to provide the best care for the patients, and that treatment should be discussed and agreed between the two parties [5]. Therefore, patient evaluation of the treatment is an important factor for its success.*

*Recently, the development of new treatments with various mechanisms and diagnosis criteria for early detection have allowed diagnosis and treatments in earlier stages of RA than previously possible [6]. However, it is a chronic condition that is still difficult to cure, and various complications [7-10] and decreased quality of life [1] can occur with insufficient treatment or a prolonged disease presence. Within 2 years of diagnosis, irreversible bone erosion has been observed in more than 50% of patients [7], and it was shown that patients with prolonged disease period have a high risk for widespread complications, such as cardiovascular conditions [8], infection [9], and malignant tumor [10].*

*According to the 2015 American College of Rheumatology Guideline, patients who have insufficient response to or who do not have tolerance to the conventional synthetic disease-modifying antirheumatic drugs (csDMARDs) as the 1st line treatment are recommended to switch to biologic DMARDs (bDMARDs) or the small molecular target therapy JAK suppressor (tofacitinib citrate) to minimize disease activity or to expedite remission [11]. Most patients who receive csDMARDs suffer from a prolonged disease period, and it is important to assess quality of life and treatment satisfaction in this population.*

*bDMARDs are injectables, and they have been reported to have low compliance [12] owing to invasive administrations and loss of therapeutic effects from immunogenic response [13, 14]. On the contrary, tofacitinib citrate, which has been developed recently and used as an antirheumatic drug, is reported to have similar efficacy [15] and safety [16-18] as those of the bDMARDs and has a higher patient preference owing to its oral route of administration [19].*

*In a comparison using a RCT, non-inferior effects [15] and safety [20] of tofacitinib citrate were shown when compared to commonly used the bDMARD adalimumab, and both agents showed a higher quality of life than the placebo [21]. However, most clinical treatment success reports compare bDMARDs [22-24], and there are few reports that compare JAK suppressors with bDMARDs and their effects on patient treatment satisfaction and quality of life.*

*Therefore, the purpose of this study is to compare the two most common clinically used antirheumatic agents, adalimumab and tofacitinib, in terms of treatment satisfaction and*

quality of life among Korean patients to assess treatment success from patients' perspectives.

## 1.1 STUDY DESIGN

This is a non-interventional, multicenter, cross-sectional, observational study. Through review of medical records, the study will analyze the comparison of treatment satisfaction and quality of life in patients with rheumatoid arthritis who have been treated with tofacitinib citrate or adalimumab between 6 months to 2 years to understand treatments in a clinical environment. Patient questionnaires will be used as part of the patients' self-reporting of results

### 1.1.1 Study Population

Subjects in this study include patients with rheumatoid arthritis at the participating institutions who have satisfied the inclusion criteria. Inclusion and exclusion criteria are defined in the study protocol.

### 1.1.2 Sample Size

*The purpose of this study is to compare treatment satisfaction and quality of life in patients with RA who are receiving adalimumab or tofacitinib citrate. It is essential to identify the minimum sample size required to obtain statistically significant differences between the two groups. The equation below was used to calculate the sample size in this study [31].*

$$N = \frac{2\sigma^2}{(\mu_1 - \mu_2)^2} [z_{1-\alpha/2} + z_{1-\beta}]^2$$

- $\sigma$ : Standard deviation from the overall satisfaction pooled  $\approx 14.58$  (SD1: 16 [18], SD2: 13 [24])

$$\sigma = \sqrt{(\sigma_1^2 + \sigma_2^2)/2}$$

- $\mu_1$ : Average of the overall satisfaction measured (larger) = 83 [24]
- $\mu_2$ : Average of the overall satisfaction measured (smaller) = 79 [24]
- $z_{1-\alpha/2}$ : 95% confidence interval (double-sided) significance = 1.96
- $z_{1-\beta}$ : 80% power threshold = 0.842

Sample size was calculated based on literature that compared the median general satisfaction number between two drugs from the TSQM and the EQ-5D index score [24].

Jobanputra P et al. (2010) reported that the median EQ-5D index score and the median overall satisfaction score from TSQM (interquartile range) at 3 months after taking the medication in the adalimumab group were 0.62 (0.59–0.76) and 83 (67–100), respectively. In contrast, these scores were 0.62 (0.52–0.76) and 79 (58–92), respectively, in the etanercept group. Based on the sample number calculated in this study, we assumed that the average scores for the EQ-5D index or TSQM would be similar to the median scores from this measurement tool. This is because the interquartile ranges were almost symmetrical to the median value. We also assumed that the difference between the 3rd interquartile and median values (or the difference between the median and the 1st interquartile values) would replace the deviation from the general EQ-5D index or TSQM scores. This is because approximately 67% of the normal distribution data falls within the average  $\pm$  1 standard deviation, whereas 50% of uniform distribution data falls within median  $\pm$  interquartile (in other words, within the interquartile range: Q1–Q3) values. Based on these assumptions, the standard deviations for the EQ-5D index scores were from 0.03 (= 0.62–0.59) to 0.14 (= 0.76–0.62) in adalimumab and from 0.1 (= 0.62–0.52) to 0.14 (= 0.76–0.62) in etanercept. Under the same assumption, the standard deviations for the TSQM scores were from 16 (= 83–67) to 17 (= 100–83) in adalimumab and from 13 (= 92–79) to 21 (= 79–58) in etanercept.

We assumed 0 (= 0.62–0.62) and 4 (= 83–79) points as the difference in the average EQ-5D and TSQM scores between patients receiving adalimumab and tofacitinib citrate. We also assumed the standard deviations as 0.03–0.14 and 16–17 points for the EQ-5D index and TSQM, respectively, in patients receiving adalimumab and in patients receiving tofacitinib citrate, the EQ-5D index and TSQM as 0.1–0.4 points and 13–21 points, respectively. Through various combinations of standard deviations, we assumed that the minimum pooled standard deviation is 0.07 (=  $\sqrt{(0.03^2 + 0.1^2)/2}$ ) and 14.58 (=  $\sqrt{(16^2 + 13^2)/2}$ ), and the maximum pooled standard deviation is 0.14 (=  $\sqrt{(0.14^2 + 0.14^2)/2}$ ) and 19.1 (=  $\sqrt{(17^2 + 21^2)/2}$ ) in the EQ-5D index and TSQM, respectively.

It was calculated that a total of 32 subjects in each group will be needed to detect the average difference of 0.05 points in EQ-5D with an 80% power at 5% significance, and a standard deviation of 0.07. The average difference of EQ-5D between the groups from a previous study was 0, which could not be used to calculate the sample size. Therefore, we voluntarily selected a small number, 0.05, as the average difference for the calculation. If 0.14 is used as the pooled standard deviation, a total of 125 per group will be needed.

When 14.58 is set as the pooled standard deviation for TSQM, a total of 209 subjects will be needed for each group for an 80% power with 5% significance. If 19.1 is set as the pooled standard deviation, a total of 359 subjects will be needed for each group.

*Based on the above calculations of the range of sample sizes for each group, the most number needed for each group, conservatively, is 360 subjects. Considering 10–20% of subjects not consenting, the actual sample size would be 400–450 subjects per group. Therefore, approximately 420 subjects will be identified from each group from the total of 840 subjects in this study.*

*Considering the geographic distribution and the number of patients as well as the clinical experiences and the academic success of the physicians, institutions participating in this study are deemed representative hospitals to care for patients with RA in Korea. Therefore, we believe that subjects who are screened from these institutions and undergo inclusion/exclusion criteria and the consent process are representative of Korea's patients with rheumatoid arthritis who either use tofacitinib citrate or adalimumab.*

### **1.1.3 Data Source**

*Once a subject satisfies the inclusion criteria and voluntarily consents to participate in the study, subject data will be collected through review of medical records and patient questionnaires. Variables collected from the medical chart include demographic and clinical characteristics. Educational status, total income for the past year, and the current employment status will be collected from the questionnaires. Treatment satisfaction and the quality of life questions will be collected using the TSQM questionnaires and EQ-5D measurements, and the subject will self-record these.*

## **1.2 STUDY OBJECTIVES**

*This study aim to compare treatment satisfaction and quality of life between patients who have been using tofacitinib citrate and patients who have been using adalimumab for 6 months or more and less than 2 year in treatment of rheumatoid arthritis.*

### **1.2.1 Primary Objective**

*To compare the treatment satisfaction between tofacitinib citrate users and adalimumab users.*

[figure not shown]
[figure not shown]
### **1.2.2 Secondary Objectives**

*To compare the quality of life between tofacitinib citrate users and adalimumab users*

## **2 INTERIM ANALYSES**

*Not Applicable*

PFIZER CONFIDENTIAL

### 3 HYPOTHESES AND DECISION RULES

[figure not shown]
#### 3.1 STATISTICAL HYPOTHESES

This is a non-interventional, multicenter, cross-sectional study intended to evaluate treatment satisfaction and quality of life in patients with rheumatoid arthritis who are taking tofacitinib citrate or adalimumab between 6 months to 2 years. Therefore, there is no statistical hypothesis.

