It was calculated that a total of 32 subjects in each group will be needed to detect the average difference of 0.05 points in EQ-5D with an 80% power at 5% significance, and a standard deviation of 0.07. The average difference of EQ-5D between the groups from a previous study was 0, which could not be used to calculate the sample size. Therefore, we voluntarily selected a small number, 0.05, as the average difference for the calculation. If 0.14 is used as the pooled standard deviation, a total of 125 per group will be needed.

When 14.58 is set as the pooled standard deviation for TSQM, a total of 209 subjects will be needed for each group for an 80% power with 5% significance. If 19.1 is set as the pooled standard deviation, a total of 359 subjects will be needed for each group.

Based on the above calculations of the range of sample sizes for each group, the most number needed for each group, conservatively, is 360 subjects. Considering 10–20% of subjects not consenting, the actual sample size would be 400–450 subjects per group. Therefore,

approximately 420 subjects will be identified from each group from the total of 840 subjects in this study.

Considering the geographic distribution and the number of patients as well as the clinical experiences and the academic success of the physicians, institutions participating in this study are deemed representative hospitals to care for patients with RA in Korea. Therefore, we believe that subjects who are screened from these institutions and undergo inclusion/exclusion criteria and the consent process are representative of Korea's patients with rheumatoid arthritis who either use tofacitinib citrate or adalimumab.

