#### 3.2 STATISTICAL DECISION RULES

- *If a statistical test is required, it should be carried out at the two-side significant level 5%.*
- *When multivariable analysis is performed, independent variables used for actual analysis can be added or subtracted considering the structure of collected data and general characteristics of study subjects.*
- *When the analysis with propensity score matching is performed, paired t-test, McNemar's test, Linear mixed model, conditional logistic regression, etc. are used for analysis.*

PFIZER CONFIDENTIAL

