### 5.1 EFFICACY/EFFECTIVENESS ENDPOINT(S)

Variable	Role	Data source	Operational definition
Treatment satisfaction	Outcome	Patient questionnaire	
 
▪ 14 questions applicable for treatment satisfaction measurement 
 
- Self-reporting questionnaire for evaluating treatment satisfaction
 
- Four domains including effectiveness, convenience, global satisfaction, and side effects
 
- Scores for each domain are calculated based on the equation
 
- Range of 0–100
 
 
 
▪ Higher numbers indicate higher treatment satisfaction
 

EQ-5D index	Outcome	Patient questionnaire	
 
▪ Standardized tool for measuring overall health
 
▪ EQ-5D index: 15 questions for assessing quality of life 
 
- Five domains, including mobility, self-care, usual activities, pain/discomfort, and anxiety/depression
 
- Scores for each domain are calculated based on the equation
 
 
 
▪ Higher scores indicate better health
 

EQ VAS	Outcome	Patient questionnaire	
 
▪ Standardized tool for measuring overall health
 
▪ EQ VAS: Value for evaluating overall health 
 
- Range of 0–100
 
 
 
▪ Higher scores indicate better health
 

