#### 7.2.3.2 Treatment Satisfaction

PFIZER CONFIDENTIAL

Treatment domains (effectiveness, side effects, convenience, and global satisfaction) will be presented as the average, standard deviation, median (interquartile range), and range (minimum, maximum). Multivariate linear regression analysis will be used to evaluate treatment satisfaction based on the demographic and clinical characteristics that affect each domain of the treatment satisfaction. However, if data involve analysis after propensity score matching, a linear mixed model will be substituted to suit the characteristics of the matched data.

[figure not shown]

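### The primary objective, treatment satisfaction, rests on four TSQM domains with none named as primary, and the SAP denies any hypothesis although the study is sized on a 4-point difference in overall satisfaction

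*SAP*

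**What the plan says.** The primary objective, in Protocol section 6 and SAP 1.2.1, is "To compare the treatment satisfaction between tofacitinib citrate users and adalimumab users". No domain is named.

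SAP 5.1 defines the outcome as "Four domains including effectiveness, convenience, global satisfaction, and side effects", each scored 0 to 100. SAP section 8 gives a separate scoring formula for each domain and no composite. SAP 7.2.3.2 summarises all four alike and adds: "Multivariate linear regression analysis will be used to evaluate treatment satisfaction based on the demographic and clinical characteristics that affect each domain". The next sentence but one of that section's logic matters too: after matching, a linear mixed model replaces the regression. SAP 7.2.4 has a single row for treatment satisfaction, again with no domain.

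On testing, SAP 3.1 says "Therefore, there is no statistical hypothesis", giving the non-interventional cross-sectional design as the reason. SAP 3.2 says that if a test is needed, "it should be carried out at the two-side significant level 5" per cent. SAP 7.1.1 lists the tests for comparing groups, and SAP 7.2.3.1 says the two matched groups will be compared on satisfaction.

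On size, Protocol 7.5 and SAP 1.1.2 say the aim is a sample large enough for a statistically significant group difference. The inputs are on one scale: "Average of the overall satisfaction measured (larger) = 83", against 79 for the smaller mean, with two-sided 5% and 80% power. The largest result sets the target: "If 19.1 is set as the pooled standard deviation, a total of 359 subjects will be needed for each group". The protocol then allows for refusal: "Considering 10–20% of subjects not consenting, the actual sample size would be 400–450 subjects per group". It settles on about 420 per group.

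**The concern.** A study that is sized to detect a stated difference at a stated error rate has a hypothesis. SAP 3.1 says it has none. The endpoint and analysis sections then leave four scores with equal standing under one primary objective. The sizing text points to the Global Satisfaction domain, but no endpoint or analysis section adopts it, so nothing binds the report to it.

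Two things are at stake.

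- **Error rate.** If a difference in any one domain can be presented as a difference in satisfaction, the 5% level does not hold for the objective.
- **Meaning of the result.** One drug is oral and the other injected. A difference confined to convenience could be presented as the answer on satisfaction, although the study was sized on overall satisfaction.

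**Working it through.** **1. The plan's own sample size.** Inputs from Protocol 7.5 and SAP 1.1.2: difference 83 − 79 = 4; pooled SD √((16² + 13²)/2) = 14.58 at the lowest and √((17² + 21²)/2) = 19.1 at the highest; z values 1.96 and 0.842. Formula: N = 2σ²/(μ1 − μ2)² × (1.96 + 0.842)².

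- SD 14.58: 2 × 14.58²/16 × 2.802² = 208.6, so 209. The plan says 209.
- SD 19.1: 2 × 19.1²/16 × 2.802² = 358.02, so 359. The plan says 359 and takes 360.
- Refusal: 360/0.90 = 400 and 360/0.80 = 450, as stated.

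The arithmetic is sound. The EQ-5D calculations in the same section give 32 and 125 per group, so overall satisfaction sets the size.

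**2. False-positive chance under any-domain reporting.** Suppose that no domain truly differs, that each of the four is tested at two-sided 5%, and that any one significant domain is reported as a satisfaction difference. With independent domains the chance is 1 − 0.95⁴ = 18.5%. The documents give no correlation between domains, so a common value is assumed. The four test statistics are treated as jointly normal, and the chance that at least one exceeds 1.96 in absolute value is:

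| Assumed correlation | Chance of at least one false positive |
|---|---|
| 0 | 18.5% |
| 0.3 | 17.4% |
| 0.5 | 15.6% |
| 0.7 | 13.0% |
| 0.9 | 9.4% |
| 0.95 | 8.0% |

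**3. Power if Global Satisfaction alone is primary.** Power = Φ(4/(σ√(2/n)) − 1.96). The other tail is negligible. The number analysed depends on how the 420 is read. If 420 are approached and 10% to 20% refuse, 420 × 0.8 = 336 to 420 × 0.9 = 378 remain. If 420 is the number enrolled, all 420 may be analysed.

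| Analysed per group | SD 19.1 | SD 14.58 |
|---|---|---|
| 336 | 77.5% | 94.5% |
| 360 | 80.2% | 95.7% |
| 378 | 82.1% | 96.5% |
| 420 | 85.9% | 97.8% |

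For example, at 360 and SD 19.1: 4/(19.1 × √(2/360)) = 2.810; 2.810 − 1.96 = 0.850; Φ(0.850) = 80.2%. These figures use the plan's unadjusted formula and allow nothing for matching or weighting.

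**4. Matching ratio (secondary).** Protocol 7.3.1 considers 1:1 matching and does not allow a subject to be used twice. SAP 7.2.3.1 assumes 2:1, with two group 1 subjects for each group 2 subject. With 420 per group, group 1 can serve at most 420/2 = 210 group 2 subjects, so at least 210/420 = 50% of group 2 is lost. SAP 7.2.3.1 permits inverse probability weighting once more than 25% of the standard group is lost. If group 2 is that group, the trigger is met before any data are seen. The documents do not say which drug is group 1 or which group is the standard one.

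**The case against.** The strongest reply is that the study is descriptive. SAP 3.1 declares no hypothesis, SAP 3.2 speaks only of a test if one is needed, and Protocol 7.9 disclaims causal evidence. On that reading there is no error rate to inflate. This stands as a limit on the size of the problem: a reader might infer that the plan's false-positive rate is 18.5%, but no passage adopts an any-domain reporting rule, and 18.5% is only the independence case. It does not remove the gap. No passage calls the domains descriptive, a significance level is set, and the primary objective would still have no designated answer.

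It can also be said that the sizing text already identifies overall satisfaction, so only a label is missing. That is largely true, and it is why the fix is cheap. The sentence in SAP 7.2.3.2 on each domain is also weaker evidence of four treatment tests than it looks, because it concerns patient characteristics and does not mention drug. The group comparison is in SAP 7.2.3.1, which names no domain at all.

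A reader might go on to infer that SAP 7.2.3.1 (matching) and SAP 7.2.4 (regression only) contradict each other outright. SAP 7.2.3.2 partly reconciles them by substituting a linear mixed model after matching. Protocol 7.7 also lets the SAP modify the protocol. What remains is that Protocol 7.7.2 lists four propensity methods and regression without ranking them, that weighting is optional once triggered, and that the matching ratios differ.

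The table shells cited in SAP section 9 are not in the text available, so they could not be checked.

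**Conclusion.** The point holds as a gap in specification and a contradiction between SAP 3.1 and the plan's own sizing. It should be corrected.

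Its size is conditional. If any one significant domain were reported as the satisfaction result, the false-positive chance would be about 8% to 18.5%, on assumed common correlations from 0.95 to 0. If the domains are purely descriptive, that figure does not apply.

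Two stronger conclusions are not supported. The sample size is not miscalculated, since the plan's figures reproduce. Nor do the documents show that the study is underpowered for Global Satisfaction: at the larger SD, power lies between 77.5% and 85.9% depending on whether 336 or 420 per group are analysed, and at the smaller SD it is at least 94.5%. Reading the overall satisfaction of the sizing text as the Global Satisfaction domain is an inference, though it is the only one of the four that fits.

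The matching-ratio point is secondary. It rests on equal groups of 420, no reuse of subjects, the 2:1 ratio being the intended one rather than an example, and group 2 being the standard group.

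**What to change.** Replace the statement in SAP 3.1 with one two-sided 5% null hypothesis: no difference in mean TSQM Global Satisfaction between the two drugs. Make effectiveness, side effects and convenience secondary, either with Holm adjustment or labelled as descriptive. Carry the same wording into SAP 5.1 and 7.2.4.

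As a secondary change, label one propensity analysis primary before outcomes are compared by drug, and call the others sensitivity analyses. Settle on one matching ratio, say which drug is group 1 and which is the standard group, and align Protocol 7.3.1 and 7.7.2 with SAP 7.2.3.1 and 7.2.4.

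The cost is mainly wording. The required size stays at 359, taken as 360 per group. A protocol amendment may be needed, because Protocol 7.7 asks for one when a primary endpoint definition or its analysis changes materially. The real downside is that a difference confined to another domain, such as convenience, can no longer be the primary result.
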